12.0 RESEARCH PARTICIPANT REGISTRATION

Confirm in the electronic medical record that the patient has received the Notice of Privacy Practice. This must be obtained before the eligibility confirmation and obtaining of the research informed consent.

- Confirm eligibility as defined in the section entitled Criteria for Patient/Subject Eligibility.
- Obtain written informed consent from each patient

13.0 DATA MANAGEMENT ISSUES

The clinical research nurse/study coordinator responsibilities include: project compliance, data collection, abstraction and entry, data reporting, regulatory monitoring, problem resolution and prioritization, and coordinate the activities of the protocol study team.

The data collected for this study will be entered into a secure database at Biomed. Source documentation will be available to support the computerized patient record.

13.1 Quality Assurance

Weekly registration reports will be generated to monitor patient accruals and completeness of registration data. Routine data quality reports will be generated to assess missing data and inconsistencies. Accrual rates and extent and accuracy of evaluations and follow-up will be monitored periodically throughout the study period and potential problems will be brought to the attention of the study team for discussion action. Random-sample data quality and protocol compliance audits will be conducted by the study team, at a minimum of two times per year, more frequently if indicated

Data collection and record keeping

13.2 Data monitoring and sponsor CRFs collection will be performed by Biomed Research. The clinical data for this protocol will be recorded on patient Case Report Forms (CRF's) printed on 3-part NCR and bound into individual patient booklets. Once all data queries are resolved for a given data form, the white copy will go to the sponsor (Trod), the yellow copy will go to MCC data management, and the pink copy will stay with the MCC clinical coordinator for study archiving. Biomed will monitor conformance to the protocol informed consent, AE's, etc. as well as verify random CRF's to source documents and work with MCC to resolve data queries. Biomed will be responsible to collect the sponsor's copy (white) of the completed/verified/signed CRF's, but Biomed will not retain sponsor CRF's.

13.2.1 Identifying patient information will be kept confidential. CRF's will not contain the patient's MRN, name, etc. only, a "Subject Record ID No (3 digits)" and "Subject Initials" (F, M, L). The Clinical Research Nurse/Coordinator at Moffitt will maintain the "key" that links patients (with their name, MRN, etc.) to their "Subject Record No." The "key" will be destroyed upon completion of data analysis for this study. Identifying patient information will be kept confidential. All direct identifying (name, medial record number, etc.) will be destroyed and removed from the computer upon completion of data analysis for this study.

13.2.2 Representatives of the IRB, OHRP, Moffitt Committees and Center for Medicare and Medicaid Services (CMS) will have access to patient information as it pertains to the study.

13.2.3 Privacy and confidentiality of the information will be protected to the extent provided by the law.

13.2.4 The Principal Investigator and the Clinical Research Nurse/Coordinator assigned to the study protocol will be primarily responsible for maintaining all study related documents including the clinical research forms, as well as for providing the sponsor with its copy of each completed CRF. All data collection will be performed on hard-copy (3-part NCR) CRF's. The review of medical records (by the study team at Moffitt) within the Cancer Center's institutional database will be done in a manner to assure that patient confidentiality (PHI) is protected and maintained at all times.

14. ETHICS/ HUMAN SUBJECT'S PROTECTION

14.1 Patient Consent: Patients who are candidates for this study at Moffitt Cancer Center will be approached for this study. Patients meeting the eligibility criteria will be consented using the IRB approved consent form. The consent will be verbally explained to the participant by a member of the research team, describing the study procedures, risks, benefits, etc. Patients must be freely consenting adults. Patients who meet eligibility criteria and provide informed consent as documented by a signed consent form by the clinical note of the consenting investigator will be enrolled in this study. All subjects interested in participating in this study will be given a copy of the informed consent form to read and sign. Each subject who is interested in participating in this study will be asked to sign and date the IRB approved consent form. All discussions related to participating in this study and obtaining informed consent will take place in a private room in the clinic at Moffitt to ensure the privacy and confidentiality of each subject is protected. Only members of the research team will be involved in this process and have access to the signed consent forms. All signed consent forms will be stored in a locked file cabinet.

14.2 Regulatory Approval: The trial will be approved by both the H. Lee Moffitt Cancer Center and Research Institute's Scientific Review Committee (SRC) and the Institutional Review Board (IRB).

14.3 Protocol Modifications: No modifications will be made to the protocol and implemented without the agreement of the investigators and approval from the Moffitt Scientific Review Committee (SRC) and the Institutional Review Board (IRB). Changes that significantly affect the safety of the patients, the scope of the investigation, or the scientific quality of the study will require approval from the SRC and IRB prior to implementation, except where the modification is necessary to eliminate apparent immediate hazard to human subjects. Any departures from the protocol will be documented in the case report form and the source documentation and reported the SRC and IRB.

- **14.4 Potential Risks:** There are risks associating with having any type of surgery. The surgery team will explain these risks to the potential participants and inform them they will be asked to sign a separate consent form for the standard of care treatment and if they agree to participate, an informed consent to participate in this research study. These risks include bleeding, infection, urinary incontinence, risk of anesthesia related complications, urinary retention, erectile dysfunction, urinary urgency, frequency and rectal fistula. There are also psychological risks associated with completing the quality of life questionnaires.

As with any research study, there is always a potential risk of unintentional disclosure of protected personal health information (PHI); however, every precaution will be taken to ensure all PHI and data collected as part of this study is kept confidential. All data will be kept confidential.

14.5: Potential Benefits: Participants will not directly benefit for taking part in this study. We hope that the results of this study will someday benefit future patients with prostate cancer.

14.6: Payment and Costs:

14.6.1: Payment

Participants will not be paid to participate in this study.

14.6.2: Costs to Participate

There will be no extra cost to patients as a result of participating in this study. Costs of standard medical care for RFA, including all costs of the surgery, lab work, etc. will be charged to the patient and/or their insurance company.

Participants and/or their insurance company will be financially responsible for hospital inpatient, outpatient and follow-up visits that would normally or routinely occur in the management of their disease. Inpatient and outpatient visits could include charges for treatments, medications, physician visits, laboratory tests and procedures. Participants and /or their insurance company will be responsible for paying for the charges which are considered routine, since they would have received these services even if they were not participating in this study. Participants will be responsible for any costs not covered by their insurance company, including deductibles, co-payments and all out-of-pocket expenses. Participants and/or their insurance company will not be responsible for paying for the following testing and procedures that are specifically required for this research study and are not considered part of the routine management of their disease, if these procedures are performed at Moffitt Cancer Center.

- Procedure: Focal Bipolar Radiofrequency ablation of the Prostate.
- 6 Month Follow up Visit: PT, PTT - bleeding (clotting) tests, Chest x-ray - A chest x-ray is a radiology test that involves exposing the chest briefly to radiation to produce an image of the chest and the internal organs of the chest. Transperineal Mapping Prostate Biopsy- A method of detecting prostate cancer in men with elevated PSA.
Electrocardiogram (EKG)-Measures the electrical function of your heart.

14.7: Confidentiality of Data: All data will be kept confidential. No names or identifying information will be included in any publications that result as conducting this study. Only data that does not include direct identifiers (such as name, MRN, etc.) will be shared with the company funding the study (Trod) or Biomed who will be monitoring this study on behalf of Trod. Although elements of dates will be shared with the sponsor, the sponsor will not be able to identify a specific subject/patient without access into Moffitt's computerized data systems.

15.0 FUNDING

Trod Medical will provide the funds and resources needed to carry out this study in accordance with MCC's internal processes and controls for investigator-initiated clinical/research studies.

APPENDIX B RECTAL ASSESSMENT SCALE -(RAS)

Date of Visit: _____ Total Score: _____

Please fill out this short questionnaire to help us find out more about any problems you may be having with diarrhea. Check the statement for each subject that best describes your situation during the past 7 days.

	0	1	2	3
Frequency of stools per day:	 0-1 Stools per day	 2 Stools per day	 3 Stools per day	 4 or more stools per day
Consistency of stools per day:	 All stools formed	 Stools formed and loose	 Stools loose	 Watery stools
Urgency of stools	 No urgency	 Somewhat urgent	 Urgent	 Very urgent
Abdominal discomfort:	 No discomfort	 Mild-moderate discomfort	 Somewhat severe discomfort	 Very severe discomfort
Hemorrhoid discomfort	 No discomfort	 Requires mild treatment (e.g. Tucks, sitz baths)	 Requires topical medication (e.g. Preparation H., etc.)	 Requires oral analgesics or narcotics for pain relief

Adapted from: RAS

Signature of Patient or Legal Representative

Date _____

Signature of Person Completing Form (if not patient)

Relationship to Patient _____

American Urological Association (AUA) Symptom Score

Please circle one number for each question.

	Not at All	Less Than 1 Time in 5	Less Than Half the Time	About Half the Time	More Than Half the Time	Almost Always
Over the past week or so, how often have you had a sensation of not emptying your bladder completely after you finished urinating?	0	1	2	3	4	5
During the past week or so, how often have you had to urinate again less than two hours after you finished urinating?	0	1	2	3	4	5
During the past week or so, how often have you found you stopped and started again several times when you urinated?	0	1	2	3	4	5
How often have you found it difficult to postpone urination?	0	1	2	3	4	5
During the past week or so, how often have you had a weak urinary stream?	0	1	2	3	4	5
During the past week or so, how often have you had to push or strain to begin urination?	0	1	2	3	4	5
During the last week, how many times did you most typically get up at night to urinate?	0	1 time	2 times	3 times	4 times	5 times

Total Score: _____

Signature of Patient or Legal Representative _____

Date: _____

Signature of Person Completing Form (If not patient) _____

Relationship to Patient: _____

04/10

EMR: GU Patient Questionnaire / Radiation Oncology Questionnaire
Page 1 of 1

PATIENT NAME: _____
MR#: _____

EPIC

The Expanded Prostate Cancer Index Composite

This questionnaire is designed to measure Quality of Life issues in patients with Prostate cancer. To help us get the most accurate measurement, it is important that you answer all questions honestly and completely.

Remember, as with all medical records, information contained within this survey will remain strictly confidential.

Today's Date (please enter date when survey completed): Month _____ Day _____ Year _____

Name (optional): _____

Date of Birth (optional): Month _____ Day _____ Year _____

URINARY FUNCTION

This section is about your **urinary habits**. Please consider **ONLY THE LAST 4 WEEKS**.

1. Over the past 4 weeks, how often have you leaked urine?

More than once a day.....	1
About once a day.....	2
More than once a week.....	3
About once a week.....	4
Rarely or never.....	5

(Circle one number)

2. Over the past 4 weeks, how often have you urinated blood?

More than once a day.....	1
About once a day.....	2
More than once a week.....	3
About once a week.....	4
Rarely or never.....	5

(Circle one number)

3. Over the past 4 weeks, how often have you had pain or burning with urination?

More than once a day.....	1
About once a day.....	2
More than once a week.....	3
About once a week.....	4
Rarely or never.....	5

(Circle one number)

4. Which of the following best describes your urinary control during the last 4 weeks?

No urinary control whatsoever.....	1
Frequent dribbling.....	2
Occasional dribbling.....	3
Total control.....	4

(Circle one number)

5. How many pads or adult diapers per day did you usually use to control leakage during **the last 4 weeks**?

None	0
1 pad per day.....	1
2 pads per day.....	2
3 or more pads per day.....	3

(Circle one number)

6. How big a problem, if any, has each of the following been for you during the last 4 weeks?

(Circle one number on each line)

	No Problem	Very Small Problem	Small Problem	Moderate Problem	Big Problem
a. Dripping or leaking urine	0	1	2	3	4
b. Pain or burning on urination.....	0	1	2	3	4
c. Bleeding with urination.....	0	1	2	3	4
d. Weak urine stream or Incomplete emptying.....	0	1	2	3	4
e. Waking up to urinate.....	0	1	2	3	4
f. Need to urinate frequently during the day	0	1	2	3	4

7. Overall, how big a problem has your urinary function been for you during **the last 4 weeks**?

No problem.....	1
Very small problem.....	2
Small problem.....	3
Moderate problem.....	4
Big problem.....	5

(Circle one number)

BOWEL HABITS

The next section is about your bowel habits and abdominal pain.
Please consider ONLY THE LAST 4 WEEKS.

8. How often have you had rectal urgency (felt like I had to pass stool, but did not) during the last 4 weeks?

More than once a day.....	1
About once a day.....	2
More than once a week.....	3
About once a week.....	4
Rarely or never.....	5

(Circle one number)

9. How often have you had uncontrolled leakage of stool or feces?

More than once a day.....	1
About once a day.....	2
More than once a week.....	3
About once a week.....	4
Rarely or never.....	5

(Circle one number)

10. How often have you had stools (bowel movements) that were loose or liquid (no form, watery, mushy) during the last 4 weeks?

Never.....	1
Rarely.....	2
About half the time.....	3
Usually.....	4
Always.....	5

(Circle one number)

11. How often have you had bloody stools during the last 4 weeks?

Never.....	1
Rarely.....	2
About half the time.....	3
Usually.....	4
Always.....	5

(Circle one number)

12. How often have your bowel movements been painful **during the last 4 weeks?**

Never.....	1
Rarely.....	2
About half the time.....	3
Usually.....	4
Always.....	5

(Circle one number)

13. How many bowel movements have you had on a typical day **during the last 4 weeks?**

Two or less.....	1
Three to four.....	2
Five or more.....	3

(Circle one number)

14. How often have you had crampy pain in your abdomen, pelvis or rectum **during the last 4 weeks?**

More than once a day.....	1
About once a day.....	2
More than once a week.....	3
About once a week.....	4
Rarely or never.....	5

(Circle one number)

15. How big a problem, if any, has each of the following been for you? (Circle one number on each line)

	No Problem	Very Small Problem	Small Problem	Moderate Problem	Big Problem
a. Urgency to have a bowel movement.....	0	1	2	3	4
b. Increased frequency of bowel movements.....	0	1	2	3	4
c. Watery bowel movements.....	0	1	2	3	4
d. Losing control of your stools.....	0	1	2	3	4
e. Bloody stools.....	0	1	2	3	4
f. Abdominal/ Pelvic/Rectal pain....	0	1	2	3	4

16. Overall, how big a problem have your bowel habits been for you **during the last 4 weeks?**

No problem.....	1
Very small problem.....	2
Small problem.....	3
Moderate problem.....	4
Big problem.....	5

(Circle one number)

SEXUAL FUNCTION

The next section is about your current sexual function and sexual satisfaction. Many of the questions are very personal, but they will help us understand the important issues that you face every day. Remember, THIS SURVEY INFORMATION IS COMPLETELY CONFIDENTIAL. Please answer honestly about THE LAST 4 WEEKS ONLY.

17. How would you rate each of the following during the last 4 weeks? (Circle one number on each line)

	Very Poor to None	Poor	Fair	Good	Very Good
a. Your level of sexual desire?.....	1	2	3	4	5
b. Your ability to have an erection?.....	1	2	3	4	5
c. Your ability to reach orgasm (climax)?.....	1	2	3	4	5

18. How would you describe the usual QUALITY of your erections during the last 4 weeks?

None at all..... 1
Not firm enough for any sexual activity..... 2
Firm enough for masturbation and foreplay only..... 3 (Circle one number)
Firm enough for intercourse..... 4

19. How would you describe the FREQUENCY of your erections during the last 4 weeks?

I NEVER had an erection when I wanted one..... 1
I had an erection LESS THAN HALF the time I wanted one..... 2
I had an erection ABOUT HALF the time I wanted one 3 (Circle one number)
I had an erection MORE THAN HALF the time I wanted one..... 4
I had an erection WHENEVER I wanted one..... 5

20. How often have you awakened in the morning or night with an erection during the last 4 weeks?

Never 1
Less than once a week..... 2
About once a week..... 3 (Circle one number)
Several times a week..... 4
Daily..... 5

21. During the last 4 weeks, how often did you have any sexual activity?

Not at all.....	1
Less than once a week.....	2
About once a week.....	3
Several times a week.....	4
Daily.....	5

(Circle one number)

22. During the last 4 weeks, how often did you have sexual intercourse?

Not at all.....	1
Less than once a week.....	2
About once a week.....	3
Several times a week.....	4
Daily.....	5

(Circle one number)

23. Overall, how would you rate your ability to function sexually during the last 4 weeks?

Very poor.....	1
Poor.....	2
Fair.....	3
Good.....	4
Very good.....	5

(Circle one number)

24. How big a problem during the last 4 weeks, if any, has each of the following been for you?

(Circle one number on each line)

	No Problem	Very Small Problem	Small Problem	Moderate Problem	Big Problem
a. Your level of sexual desire.....	0	1	2	3	4
b. Your ability to have an erection.....	0	1	2	3	4
c. Your ability to reach an orgasm.....	0	1	2	3	4

25. Overall, how big a problem has your sexual function or lack of sexual function been for you during the last 4 weeks?

No problem.....	1
Very small problem.....	2
Small problem.....	3
Moderate problem.....	4
Big problem.....	5

(Circle one number)

HORMONAL FUNCTION

The next section is about your hormonal function. Please consider **ONLY THE LAST 4 WEEKS**.

26. Over the last 4 weeks, how often have you experienced hot flashes?

More than once a day..... 1
About once a day..... 2
More than once a week..... 3 (Circle one number)
About once a week..... 4
Rarely or never..... 5

27. How often have you had breast tenderness during the last 4 weeks?

More than once a day..... 1
About once a day..... 2
More than once a week..... 3 (Circle one number)
About once a week..... 4
Rarely or never..... 5

28. During the last 4 weeks, how often have you felt depressed?

More than once a day..... 1
About once a day..... 2
More than once a week..... 3 (Circle one number)
About once a week..... 4
Rarely or never..... 5

29. During the last 4 weeks, how often have you felt a lack of energy?

More than once a day..... 1
About once a day..... 2
More than once a week..... 3 (Circle one number)
About once a week..... 4
Rarely or never..... 5

30. How much change in your weight have you experienced during the last 4 weeks, if any?

Gained 10 pounds or more..... 1
Gained less than 10 pounds 2
No change in weight..... 3 (Circle one number)
Lost less than 10 pounds 4
Lost 10 pounds or more..... 5

31. How big a problem **during the last 4 weeks**, if any, has each of the following been for you?

(Circle one number on each line)

	No Problem	Very Small Problem	Small Problem	Moderate Problem	Big Problem
a. Hot flashes.....	0	1	2	3	4
b. Breast tenderness/enlargement..	0	1	2	3	4
c. Loss of Body Hair.....	0	1	2	3	4
d. Feeling depressed.....	0	1	2	3	4
e. Lack of energy.....	0	1	2	3	4
f. Change in body weight	0	1	2	3	4

Overall Satisfaction

32. Overall, how satisfied are you with the treatment you received for your prostate cancer?

Extremely dissatisfied..... 1
Dissatisfied..... 2
Uncertain..... 3 (Circle one number)
Satisfied..... 4
Extremely satisfied..... 5

THANK YOU VERY MUCH!!

APPENDIX E

 ID: _____ - _____
 Site _____ Subject _____

 INITIALS: _____
 F _____ M _____ L _____

Medical Resource Utilization Patient Diary
Patient Instructions:

Please complete the form below weekly by providing detail on non-study related health care visits. If there were multiple visits within a single week, please list out each individual visit.

Date	Did you have a health care visit this week (Y/N)?	If yes, how many healthcare visits did you have this week, and where did you visit?	For each of the visits, who did you see during this visit? (e.g., nurse, physician assistant, or physician)	What was the primary reason for this visit?	Did the healthcare personnel say the visit was related to the RFA procedure ¹ (Y/N)?	What treatment did you receive during this visit, if any?
Week 1:						
Week 2:						
Week 3:						
Week 4:						
Week 5:						
Week 6:						
Week 7:						
Week 8:						
Week 9:						
Week 10:						
Week 11:						
Week 12:						

1. Note to MCC clinical coordinator: If the patient's response to this question is "Y" an AE form must also be completed.

ID: _____ - _____
Site _____INITIALS: _____
F _____ M _____ L _____

Medical Resource Utilization Patient Diary

Patient Instructions:

Please complete the form below weekly by providing detail on non-study related health care visits. If there were multiple visits within a single week, please list out each individual visit.

Date	Did you have a health care visit this week (Y/N)?	If yes, how many healthcare visits did you have this week, and where did you visit?	For each of the visits, who did you see during this visit? (e.g., nurse, physician assistant, or physician)	What was the primary reason for this visit?	Did the healthcare personnel say the visit was related to the RFA procedure ¹ (Y/N)?	What treatment did you receive during this visit, if any?
Week 13:						
Week 14:						
Week 15:						
Week 16:						
Week 17:						
Week 18:						
Week 19:						
Week 20:						
Week 21:						
Week 22:						
Week 23:						
Week 24:						

1. Note to MCC clinical coordinator: If the patient's response to this question is "Y" an AE form must also be completed.

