After enrollment, patients will undergo endo-rectal, multi-parametric 1.5 Tesla MRI with Dynamic contrast enhancement and Diffusion Weighted images. Areas on MRI that have a high level of suspicion for prostate cancer will be identified (right or left, Central or peripheral gland) and categorized from 1 Negative to 5 highly suspicious.

For study purposes, the prostate is divided into four regions: RIGHT CENTRAL, RIGHT PERIPHERAL, LEFT CENTRAL and LEFT PERIPHERAL. Patients must meet the original entry criteria on this repeat mapping biopsy and have unilateral prostate cancer. If the patients meet the mapping-biopsy enrollment criteria, they are treated with **focal bipolar radiofrequency ablation (RFA)** meaning RFA of the sites where the biopsies were positive but no more than one prostate side. Efficacy is defined as negative biopsy cores at the sites of the focal ablation on repeat extended biopsies at 6 months after RFA. A second MRI will be performed just prior to the 6 month repeat saturation biopsy performed identical to the original pre-treatment biopsy.

At baseline (prior to pre-treatment biopsy) and at 6 months (prior to the repeat biopsy used to define efficacy) the patient will complete an American Urologic Association lower urinary tract symptom score assessment (AUA score), Rectal Assessment Scale (RAS), International Index of Erectile Function (IIEF-5), and the EPIC quality of life questionnaires.

Following completion of the focal prostate radio-frequency ablation study at 6 months from treatment, patients will undergo standard/routine care including serum PSA level every 6 months and as needed digital rectal examinations; any future prostate biopsies will be performed at the discretion of the treating physician.

Patients will also be required to complete a medical resource utilization (MRU) form to capture resource utilization between study visits, which can be used to estimate costs associated with procedure related complications and health care visits. Patients will be requested to complete a weekly diary of medical resource utilization to limit recall bias that may occur between study visits.

SCHEMA

SCHEDULE OF EVALUATIONS / STUDY CALENDAR

Parameter	Prestudy	Week 0	Week 6	3 months	6 months	End of Study Visit
History	X					
Physical examination including DRE	X		X	X	X	
QOL questionnaires (EPIC,IIEF,AUA,RAS)	X				X	
MRU (Recording weekly by patients; collected at the following visits by study coordinator)			X	X	X	

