7.0 EVALUATION DURING TREATMENT/INTERVENTION

Before any study procedures are performed (which includes all screening procedures, pre-treatment, treatment/intervention procedures, etc.), all patients will be asked to sign an informed consent form.

Focal bipolar RFA will be done (after 4 weeks and no more than 12 weeks of initial mapping biopsy): a separate informed consent for this procedure will be obtained (which is separate from the informed consent to participate in the study), per the Cancer Center's policy for any procedure conducted for treatment/diagnosis. If the laboratory studies obtained at the pre-mapping biopsy assessment are still valid (within 6 months), they will not be repeated.

Six weeks after focal bipolar RFA; DRE, PSA, assessment of toxicity will be done. Toxicity of transperineal prostate biopsy includes bleeding, infection, urinary retention. Toxicity of focal bipolar RFA includes bleeding, infection, urinary incontinence, urinary retention, erectile dysfunction, urinary urgency, urinary frequency and rectal fistula.

Three months after focal RFA; DRE, PSA, assessment of toxicity will be done as mentioned in the preceding paragraph.

Six months after focal bipolar RFA; DRE, PSA, QOL questionnaire, assessment of toxicity; obtain serum electrolytes, UA, EKG and chest x-ray in preparation for repeat mapping biopsy to be done. The patient will be scheduled for the second MRI imaging and transrectal-guided mapping prostate biopsy # 2 to be completed within 6-8 months after focal bipolar RFA. After a biopsy is requested we will have a patient follow up in 1-2 weeks for discussion of results and assessment of any adverse events (this will be the end of study visit).

Patients will record weekly medical resource utilization data to share with their study coordinator at routine scheduled visits.

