8.0.3 Study therapy is the required treatment or procedure defined on the

protocol.

8.0.4 Non-protocol therapy is defined as any treatment or procedure not described in the protocol

8.1 Adverse event assessment:

8.11 The type of event using NCI Common Toxicity Criteria for Adverse Events (CTCAE) version 4.0 will be identified and graded for severity.

8.12 The relationship of the adverse event to the therapy or procedure will be determined as follows: Unrelated; Unlikely; Possible; Probable; Definite

8.13 For reporting purposes, an adverse event is considered unexpected when either the type of event or severity of the event is not listed in the study consent

8.2 Serious Adverse Events (SAEs):

8.2.1 All study-related, unexpected Grade 3 or 4 SAEs will be immediately reported to the IRB. These toxicities will be reviewed by the principal investigator and appropriate measures taken in terms of delaying, modifying or stopping therapy.

8.2.2 The descriptions and grading scales found in the revised NCI Common Terminology Criteria for Adverse Events (CTCAE) version 4.0 will be utilized for adverse event reporting (<http://ctep.cancer.gov/reporting/ctc.html>).

8.2.3 SAEs must be followed until resolution or deemed irreversible.

8.3 Routine reporting:

8.3.1 Serious and/or unexpected adverse events will be reported to the IRB according to current IRB policy as well as Moffitt's Protocol Monitoring Committee (PMC) according to current PMC policy.

8.4 Potential Adverse Events that may occur as part of conducting this study include:

Transperineal prostate biopsy:

- Bleeding
- Infection
- Urinary retention

Focal Bipolar RFA

- Bleeding

- Infection
- Urinary Incontinence
- Urinary Retention
- Erectile Dysfunction
- Urinary Urgency
- Urinary Frequency
- Rectal Fistula

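### The resource-use diary does not define which visits patients should record, and its 24 weekly rows may end about two weeks before the 6-month cost window does

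*Combined protocol and SAP*

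**What the plan says.** Each of the two diary pages in Appendix E opens with the same instruction: "Please complete the form below weekly by providing detail on non-study related health care visits". The term is not defined there, in Section 3.4 or under Analysis of Tertiary Endpoint.

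The first question on the form asks, without any limit, whether there was a health care visit that week. A later column asks: "Did the healthcare personnel say the visit was related to the RFA procedure". A footnote tells the coordinator that if the patient answers yes, "an AE form must also be completed". The rows run from Week 1 to Week 12 on one page and from Week 13 to Week 24 on the other. The form does not say on which day Week 1 begins.

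The study summary at the front of the protocol gives the purpose of the form: "to capture resource utilization between study visits, which can be used to estimate costs associated with procedure related complications and health care visits". It says the weekly diary is there "to limit recall bias that may occur between study visits". Analysis of Tertiary Endpoint counts visits from both the diary and the adverse event form. It costs them by indication and by what was done, over a 6-month period after RFA. The study calendar has the coordinator collect the diary at week 6, 3 months and 6 months, the same visits at which toxicity is assessed.

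**The concern.** The diary is completed by the patient at home, so that patient's reading of one sentence decides what is recorded. Read as 'not caused by the study', the instruction excludes visits for complications of the ablation. Those are the visits the study summary wants costed and the RFA column is there to identify. Visits left out at the time may not be recoverable later with the detail that costing needs.

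The second issue is coverage. If the diary has no row for the last weeks of the cost window, visits in those weeks have no set place to be written down, and an average over 6 months would treat them as weeks without use. Both problems push the estimated average cost of care after RFA downwards.

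**Working it through.** **1. What the instruction can mean**

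| Source | What it suggests |
|---|---|
| Appendix E, instruction | Undefined; open to both readings |
| Appendix E, first question | Any visit in the week |
| Appendix E, RFA column and footnote | Visits related to RFA are expected on the form |
| Study summary | Use between study visits, including procedure-related complications |
| Analysis of Tertiary Endpoint | Health care visits, with no exclusion |
| Section 8.2.1 | A causal use of a similar term: "All study-related, unexpected Grade 3 or 4 SAEs will be immediately reported to the IRB" |

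Four of the six point to 'outside the scheduled study visits', one is neutral, and one shows that a causal sense also occurs in the protocol. The intended meaning can be inferred from the protocol, but the patient is handed the form, not the protocol.

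**2. What would catch an omitted visit**

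- The diary footnote starts an adverse event form only after the patient has listed the visit and answered yes. An omitted visit does not start it by that route.
- Otherwise the event must come up at a toxicity assessment. Section 7.0 sets the first one: "Six weeks after focal bipolar RFA; DRE, PSA, assessment of toxicity will be done". Others follow at 3 and 6 months. Taking 3 months as 13 weeks and 6 months as 26 weeks, the recall periods are 6 - 0 = 6 weeks, 13 - 6 = 7 weeks and 26 - 13 = 13 weeks.
- Section 7.0 and the study calendar add an End of Study visit with adverse event assessment, 1-2 weeks after a biopsy done at 6-8 months. For the weeks after Week 24, recall to the 6-month visit is only about 26 - 24 = 2 weeks.
- Adverse event collection covers adverse events, not all health care visits.

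**3. Row coverage against the cost window**

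Inputs: 24 rows (Appendix E); a 6-month window (Analysis of Tertiary Endpoint); 20 patients (Section 11.2). Assumptions: Week 1 begins at RFA, and all 20 patients are followed to 6 months. The diary covers 24 × 7 = 168 days.

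| Meaning of 6 months | Weeks | Shortfall | Share of the window |
|---|---|---|---|
| 4-week months | 6 × 4 = 24 | 0 | 0 |
| 26 weeks | 26 | 26 - 24 = 2 weeks | 2/26 = 7.7% |
| Calendar months | 365.25/2 = 182.6 days; 182.6/7 = 26.1 | 182.6 - 168 = 14.6 days = 2.1 weeks | 2.1/26.1 = 8.0% |

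In the 26-week case, 20 × 26 = 520 patient-weeks, of which 20 × 24 = 480 have a row and 40 do not (40/520 = 7.7%). These are shares of patient-weeks. The documents give no visit rates, visit timing or unit costs, so they cannot be converted to a share of cost. The proportion of RFA-related visits that the wording would cause to be omitted cannot be derived either.

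**The case against.** The form goes a long way towards explaining itself. The RFA column would have little purpose if RFA-related visits were to be left out, and the first question is unrestricted. The causal use in Section 8.2.1 is an instruction to investigators about reporting to the IRB. Nothing shows that patients see it, so it is weak evidence of how they would read a diary. This stands. A reader might infer that the diary contradicts its own purpose or excludes complications by design; the documents do not support that.

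Adverse events are also collected independently of the diary. Section 8.0.1 defines them regardless of relatedness, they are assessed at four visits including End of Study, and the coordinator goes through the diary with the patient. The gravest complications are stopping events under the stopping rules and are unlikely to come to light only through a diary. This also stands and limits the loss. It does not cover visits that are not adverse events. Whether the adverse event form records who was seen and what was done cannot be judged, because that form is not in the documents; its absence is not held against the plan.

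The row shortfall depends on assumptions. Two pages of 12 rows match two quarters of 4-week months exactly, and no start day is given for Week 1. Both points are accepted, and the zero-gap case is reported as one of the three.

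A reader might go the other way and argue that the rows should reach the End of Study visit, which would make the gap much longer. The documents do not support that: the cost window is stated as 6 months, and the last scheduled diary collection is at the 6-month visit.

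**Conclusion.** The point holds as a minor defect in a data-collection form. The instruction is ambiguous, its likely meaning can be inferred, and some patients may still leave out visits for RFA complications. The rows fall 2 to 2.1 weeks short (7.7% to 8.0% of patient-weeks) if Week 1 starts at RFA and 6 months means 26 weeks or calendar months.

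The effect is mainly a possible underestimate in a descriptive tertiary analysis. A reader might infer that about 8% of cost is lost; that does not follow. Nor is it quite right that nothing outside the cost analysis is touched. A yes in the RFA column requires an adverse event form, and adverse events feed the secondary safety summary in Section 11.5. An omitted visit could therefore remove one route by which an event is reported. Because scheduled assessments provide other routes, the link is small and does not raise the severity.

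**What to change.** - On both pages of Appendix E, replace the instruction with: *List every health care visit other than scheduled study visits, including any visit for a problem that may be related to the RFA.*
- State on the form that Week 1 begins on the day of RFA.
- Add rows through the 6-month visit: Weeks 25 and 26, plus one row for the final partial week, since six calendar months is 26.1 weeks. Alternatively, keep 24 rows and state the cost window under Analysis of Tertiary Endpoint as 24 weeks.

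The cost is one sentence printed twice, one line on the start day, and three rows or one changed phrase. No visits, procedures or patients are added. Section 14.3 requires SRC and IRB approval for protocol modifications, so the change is best made before diaries are handed out.
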